13.1.3 Phase I Waiting Periods

Dose escalation on the phase I portion of this study should not occur until a sufficient waiting period has occurred after patients have been treated. A period of 90 days must pass in order to assess toxicity. If 90 days have transpired without DLT in each

of the first seven (7) patients enrolled to a specific dose level, then dose escalation to the next level may proceed. Patients will continue to be enrolled to each dose level (up to a maximum of 15 patients) with ongoing assessment of those reaching 90 day follow-up so long as either criteria for defining the MTD (section 13.1.2) or criteria for further dose escalation is not reached. If fifteen patients are enrolled to a given dose level yet criteria for adequate follow-up are not reached in a representative sample of patients (section 13.1.2), further enrollment to the protocol will be suspended until adequate follow-up is reached.

13.2 Phase II Study Endpoints

Patients will be treated at either the MTD or highest dose from the phase I study.

13.2.1 Primary Endpoint

Late severe GU and GI toxicity is defined as grade 3-5 GU and GI toxicity occurring between 270-540 days (i.e., 9-18 months) from the start of the protocol treatment. It is graded based on CTCAE v3.0. Grade 3-5 GU or GI toxicity that originally occurred prior to 270 days from start of protocol treatment will only be considered late severe GU or GI toxicity if it persists at a severity grade of 3-5 based on CTCAE v3.0 after 270 days.

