6.1.2 Dose Fractionation

Patients will receive 5 fractions of radiation. A minimum of 36 hours and a maximum of 8 days should separate each treatment. No more than 3 fractions will be delivered per week (7 consecutive days). Total dose will depend on the phase of the study (see schema).

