10.2 Follow-up Schedule

10.2.1 Initial follow-up visit at 1.5 months from the end of treatment.

10.2.2 After initial follow-up visit, follow-up will be done at 3, 6, 9, and 12 months post therapy.

10.2.3 Then every six months until three years post treatment.

10.2.4 Then annually for years 3-10.

10.2.5 A bone scan will be performed on any patient who presents with complaints of bone pain that cannot be attributed to any intercurrent disease. Discretionary plain films may be needed to evaluate lesions seen on bone scan to confirm the diagnosis of metastatic disease.

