11.1 Summary of Data Submission

Item	Due
Demographics	Within 2 weeks of study entry
Eligibility and Entry Characteristics including baseline H&P and PSA	Within 2 weeks of study entry
Pathology Report	Within 2 weeks of study entry
AUA and EPIC baseline forms	Within 2 weeks of study entry
SBRT dosimetry information	Within 1 week after completion of SBRT
Follow-up H&P data including PSA	After last SBRT treatment, post SBRT follow-up at 1.5, 3, 6, 9, 12 months, then every 6 months to 3 years; then annually for years 3-10

AUA and EPIC post treatment forms

After last SBRT treatment, post SBRT follow-up at 1.5, 3, 12, and 18 months

Adverse Event assessment

After each SBRT treatment, then post SBRT follow-up at 1.5, 3, 6, 9, and 12 months, then every 6 months to 3 years; then annually for years 3-10

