13.5 Analysis Plan

Interim Reports: Interim reports will be prepared every six months until the results of the study are published. In general, the interim reports will contain information about patient accrual rate with projected completion dates of the trial, status of QA review and compliance rate of treatment per protocol, and the frequencies and severity of toxicity.

13.5.2 *The Analysis of Severe Late GU/GI Toxicity:* This analysis will be carried out when each patient has had at least 270 days (i.e., 9 months) of follow-up after the end of the acute period, a total of 540 days (i.e., 18 months) of follow-up. The time to the occurrence of severe late GU/GI toxicity is defined as the time interval from start of protocol treatment to the date of onset of grade 3-5 GU/GI toxicity. The time analysis for recording severe late GU/GI toxicity for this protocol will be limited to 540 days from start of protocol therapy. If no such toxicity is observed before the time of the analysis, the patient will be censored at the time of the analysis. The hazard rate will be estimated by the life table approach with a time span of 18 months. The one-sided Z-test will be used to test the significance of the difference between the logarithm of the observed hazard rate and the logarithm of the hypothesized hazard rate of 0.006/month with variance equal to the reciprocal of the number of cases with late toxicity observed. Because of the lead time of 9 months for the acute period, the 18-month late toxicity will be estimated by the 9-month toxicity rate using the cumulative incidence approach [37] to the defined time to severe late GU/GI toxicity.

13.5.3 *Estimation of Secondary Endpoints Related to the Efficacy:* Cumulative incidence approach [37] will be used to estimate the failure rate for biochemical, disease-specific, local-regional and distant failures. Kaplan-Meier method [38] will be used to estimate the overall survival rate.

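### The 18-month toxicity visit falls after the day-540 primary window closes, and the censoring rule credits unobserved event-free time to patients who have not had that visit (minor)

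*Combined protocol and SAP*

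**What the plan says.** The primary endpoint (13.2.1) is grade 3-5 GU or GI toxicity "occurring between 270-540 days (i.e., 9-18 months) from the start of the protocol treatment".

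The visit clock in 10.2 starts at the other end of the course: "Initial follow-up visit at 1.5 months from the end of treatment". The schedule goes on: "After initial follow-up visit, follow-up will be done at 3, 6, 9, and 12 months post therapy", and "Then every six months until three years post treatment". The adverse-event line in 11.1 follows the same calendar: "After each SBRT treatment, then post SBRT follow-up at 1.5, 3, 6, 9, and 12 months, then every 6 months to 3 years". Appendix I likewise moves from 12 to 18 months. No visit tolerance is given anywhere.

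Section 13.5.2 contains four relevant rules:
- The analysis is carried out once each patient has at least 540 days of follow-up (13.4.1 says the same).
- Time to event ends at the date of onset.
- The time analysis stops at day 540.
- For patients without an event: "If no such toxicity is observed before the time of the analysis, the patient will be censored at the time of the analysis".

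The section does not say how to handle a patient whose last toxicity assessment came before day 540.

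**The concern.** The window and the visits use different time origins and are never reconciled. A reader would expect the 18-month visit to close an endpoint labelled 9-18 months, but that visit comes after the cut-off. A patient last assessed at month 12 can therefore be carried to day 540 as event-free although nobody has asked about the intervening months.

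This acts on the hazard estimate in 13.5.2 in two ways. An unseen event is missing from the numerator, and the unobserved time is added to the denominator. Both lower the estimated late-toxicity rate, which in a safety trial favours the treatment. At a true rate of 23%, 47 patients yield only 47 x 0.23 = 10.8 expected events, so one or two missed events are not negligible.

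**Working it through.** **The plan's own figures.** The plan equates 270 and 540 days with 9 and 18 months, which implies 30-day months (540/30 = 18). The 47 patients can be reproduced from 13.3.2. Events are (1.645 + 1.282)^2 / ln(0.015/0.006)^2 = 10.2, so 11 (the plan states 12). Patients are 11 / (1 - exp(-0.015 x 18)) = 46.5, so 47, and 47/0.95 gives 50.

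**Course length.** From 6.1.2: "A minimum of 36 hours and a maximum of 8 days should separate each treatment", with at most three fractions in any seven days.
- Longest course: 4 x 8 = 32 days.
- Shortest course: fractions on days 0, 1.5, 3, 7 and 8.5, so about 8.5 days.

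**Visit days from the start of treatment.** Day = months x (30 or 30.44) + course length.

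| Visit | Earliest | Latest |
|---|---|---|
| 12 months | 12 x 30 + 8.5 = 368.5 | 12 x 30.44 + 32 = 397 |
| 18 months | 18 x 30 + 8.5 = 548.5 | 18 x 30.44 + 32 = 580 |

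The 18-month visit is thus 8.5 to 40 days after day 540 in every case. The stretch after the last in-window visit is 540 - 397 = 143 to 540 - 368.5 = 171.5 days, which is 53% to 64% of the 270-day window.

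**(a) Patients analysed before their 18-month visit.** If the data are cut when the last patient reaches day 540, only those who started within the preceding 8.5-40 days still await the visit. Section 13.3.2 gives three to four years for accrual and 13.4.1 gives three to five years for the study. With 50 patients accruing evenly:
- 3 years, 40-day lag: 50/1096 x 40 = 1.8 patients.
- 5 years, 8.5-day lag: 50/1826 x 8.5 = 0.2 patients.

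Taken one by one at even spacing (a start every 22 to 37 days), this means the last patient and at most one more. The number is zero if the analysis runs a few weeks later, which the plan permits.

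**(b) Patients who miss the visit or are lost.** Their number is not in the documents. For one patient last seen at month 12, assume a 23% rate, uniform onset across the window and no report by any other route. The expected missed events are then 0.23 x 0.53 = 0.12 to 0.23 x 0.64 = 0.15. Loss before month 12 costs more.

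**Effect on the test (illustrative).** The plan's test is a Z-test on the log hazard. As a simple stand-in, take the binomial cut of 9 or more of 47. This is the smallest count with one-sided error below 0.05 at a 10% rate: probability 0.041, against 0.093 for 8 or more. With all patients fully observed at 23%, the chance of 9 or more is 0.785. Now let two patients each have event probability 0.23 x (1 - gap share x share missed), with gap share 0.53-0.64:

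| Share of gap events missed (assumed) | Chance of 9 or more of 47 |
|---|---|
| 10% | 0.78 |
| 25% | 0.78 |
| 50% | 0.77 |
| 100% | 0.76 |

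**The case against.** The strongest reply is that a visit shortly after the window closes is where one would want it. Since 13.5.2 times events by onset, an assessment at day 549-580 covers the whole stretch back to the 12-month visit, whereas one before day 540 would leave a tail. **This stands**, and it limits the point. A reader might infer that more than half the window is unobserved for all 47 patients, that they are all simply counted as event-free through it, and that power falls heavily. The documents do not support that. It would require that almost nobody has an 18-month visit before the analysis, which the accrual period rules out.

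Second, 13.5.2 already caps the time analysis at day 540, so censoring at the analysis date does not credit time beyond the window. **This stands too**, but the cap does nothing for a patient last assessed well before day 540.

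Third, the plan asks for 540 days of follow-up on each patient and allows 5% for ineligible and lack-of-data cases. **This stands only in part.** The allowance sets the number enrolled. It does not say how a partly followed patient is censored.

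Fourth, 6.10.1 requires grade 3-5 events and events leading to hospitalisation to be reported, which can reach the investigator between visits. **This reduces the loss but does not remove it.** The 48-hour clock starts when the investigator becomes aware, and beyond 30 days after discontinuation only events considered probably related are covered. The endpoint definition in 13.2.1 states no attribution condition.

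**Conclusion.** The point holds as a minor one. The timing mismatch is certain for nominal visit dates, though a site could schedule the visit early because no tolerance is stated. The censoring rule is incorrect for any patient whose last assessment precedes day 540.

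The consequence is confined to the two groups above, and its direction is towards a lower late-toxicity rate. Its size cannot be derived from the documents, because they give neither the number of missed visits nor the share of events reported between visits. It ranges from nothing, if every 18-month visit is kept and used, to a small loss. The 0.76-0.78 result rests on even accrual, two affected patients, uniform onset and a binomial cut that is not the protocol's test. More frequent missed visits would make the loss larger.

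**What to change.** Amend 13.5.2, and 13.4.1 to match:
- Run the primary analysis once every patient has had, or has definitively missed, the 18-month post-therapy visit.
- At that visit, record the onset date of each grade 3-5 GU/GI event, and count those with onset by day 540.
- Censor patients without an event at their last adverse-event assessment or day 540, whichever is earlier, in place of the analysis date.

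The cost is wording, a delay of a few weeks in the primary analysis, and slightly less person-time. No visits are added.

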13.2.2 Secondary Endpoints

- Acute severe GU and GI toxicity is defined as grade 3-5 toxicity occurring prior to 270 days from the start of protocol treatment. It is graded based on CTCAE v3.0.
- Non GU and GI toxicity.
- Biochemical failure RTOG-ASTRO definition (also known as Phoenix definition) - Thus, when the PSA rises by more than 2 ng/ml above the lowest level (nadir) achieved after treatment, biochemical failure has occurred and the date of the failure is recorded at the time the nadir plus 2 ng/ml level is reached.
- Overall survival
- Disease-specific survival
- Clinical progression including local/regional and distant relapse

13.3 Sample Size

13.3.1 Overview: The primary goal of this study is to estimate the rate of late grade 3-5 genitourinary and gastrointestinal toxicity following treatment with stereotactic body radiation therapy. For purposes of this phase II study, late toxicity will be defined as toxicity occurring 270-540 days (i.e., 9-18 months) from the start of radiotherapy. It is graded based on CTCAE v 3.0.

13.3.2 Sample Size Derivation: The phase II component of this study is designed to test whether late GU/GI toxicity at 270-540 days from the start of treatment following the protocol treatment is above 10%. The sample size is determined so that the probability of rejecting the treatment because of excessive late toxicity is 90% if the true late toxicity rate is 23% or higher. Assuming an exponential distribution for time from the end of the acute period (*270 days from the start of protocol treatment*) to the occurrence of late toxicity, the hazard rate for the expected 10% toxicity rate and the unacceptable 23% toxicity rate is 0.006/month and 0.015/month, respectively. Following the asymptotic property of the observed hazard and using Z-test for the logarithm of the hazard ratio [35-36], we require 12 cases with severe late GU/GI toxicity. Thus, 47 patients are required to be accrued within three to four years and be followed for 270 days after the acute period (i.e., a total of 540 days) to have a statistical power of 90% with a one-sided significance level of 0.05. Considering 5% ineligible cases and lack-of-data cases, the sample size of the phase II component of this study is 50 patients. Patients treated in phase I at the dose level ultimately used in phase II will be included in the phase II analysis as part of the 50 patient trial.

The sample size of the phase II component of this study will not exceed 50 patients.

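### With 47 patients the planned late-toxicity test has about 78-82% power at a 23% rate, not 90%; separately, 12 cases do not convert to 47 patients

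*Combined protocol and SAP*

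**What the plan says.** Section 13.3.2 tests a late severe GU/GI toxicity rate of 10% against 23% at a one-sided level of 0.05, and promises that "the probability of rejecting the treatment because of excessive late toxicity is 90% if the true late toxicity rate is 23% or higher". It turns the two rates into hazards of 0.006 and 0.015 per month. It starts the clock at day 270 ("Assuming an exponential distribution for time from the end of the acute period"), invokes the asymptotic behaviour of the log hazard, and concludes "we require 12 cases with severe late GU/GI toxicity. Thus, 47 patients are required to be accrued within three to four years". A 5% allowance takes 47 to 50, and "The sample size of the phase II component of this study will not exceed 50 patients".

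Section 13.5.2 defines the test. Time runs from the start of treatment, and recording of events "will be limited to 540 days from start of protocol therapy". "The hazard rate will be estimated by the life table approach with a time span of 18 months". The log of the observed hazard is compared with the log of 0.006/month by a one-sided Z-test "with variance equal to the reciprocal of the number of cases with late toxicity observed".

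Under section 13.2.1, a toxicity that began before day 270 "will only be considered late severe GU or GI toxicity if it persists at a severity grade of 3-5" beyond that day.

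**The concern.** The power statement rests on a large-sample formula that treats the number of events as fixed at its expected value. Here about 11 events are expected, the count varies from trial to trial, and both the hazard estimate and its variance depend on it. Neither section reports an exact or simulated check.

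Two further details do not fit. Twelve cases do not lead to 47 patients at a 23% rate. And the printed hazards match 10% and 23% only over 18 months, whereas section 13.3.2 starts the exponential at day 270, which leaves 9 months.

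Rejecting a regimen with 23% late severe toxicity is the sizing criterion for phase II. If the true power is lower, a non-rejection is weaker reassurance than the protocol implies.

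**Working it through.** **Inputs.** From 13.3.2: rates 10% and 23%, hazards 0.006 and 0.015/month, one-sided 0.05, 47 patients, 12 cases, 540 days of follow-up. From 13.5.2: test statistic Z = √d · ln(observed hazard / 0.006), where d is the number of late cases; reject if Z > 1.645.

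**1. The plan's own figure.**
- Required events: (1.645 + 1.282)² / (ln HR)². With HR = 0.015/0.006 = 2.5 this is 10.2. With HR = ln 0.77 / ln 0.90 = 2.48 it is 10.4. Rounded up: 11.
- Event probability over 18 months: 1 − exp(−0.015 × 18) = 0.2366. Then 11/0.2366 = 46.5, so 47 patients; 47/0.95 = 49.5, so 50.
- Expected events with 47 patients: 47 × 0.23 = 10.8, or 47 × 0.2366 = 11.1. Large-sample power, Φ(√d · ln HR − 1.645), is 0.91-0.92.

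So 47 patients and 90% power reproduce as asymptotic figures, from 11 events.

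**2. The printed 12.** 12/0.2366 = 50.7 (51 patients) and 12/0.23 = 52.2 (53 patients), not 47. Two-sided testing gives 13 events. Following patients through a 36-48 month accrual period gives 26-37 patients for 12 events. No variant tried links 12 to 47. At a 23% rate, P(12 or more of 47) = 0.39.

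**3. The specified test, 18-month clock, onsets after day 270.** Each case loses about 4.5 months of exposure, so person-time ≈ 47 × 18 − 4.5d.
- d = 8: 8/810 = 0.00988/month; Z = √8 · ln(0.00988/0.006) = 1.41. No rejection.
- d = 9: 9/805.5 = 0.01117/month; Z = √9 · ln(0.01117/0.006) = 1.87. Rejection.
- Exact binomial, n = 47: P(≥9 | 0.10) = 0.041; P(≥9 | 0.23) = 0.785. Power reaches 0.90 at a true rate of 0.262.
- A cut-off of 8 would give size 0.093 and power 0.877, so no count cut-off at 47 gives 90% power with size at most 0.05.

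**4. Simulation with individual exposure times (200,000-300,000 trials per row).**

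| Reading | n | Size at 10% | Power at 23% |
|---|---|---|---|
| 18-month clock, onsets after day 270 | 47 | 0.041-0.042 | 0.783-0.785 |
| 18-month clock, constant hazard from start | 47 | 0.043 | 0.787 |
| Day-270 clock, null −ln(0.9)/9 = 0.0117 | 47 | 0.056 | 0.815 |
| Day-270 clock, printed null 0.006 | 47 | 0.411 | 0.982 |
| 18-month clock, half of cases early-onset and persistent | 47 | 0.042 | 0.787 |
| 18-month clock, all cases early-onset and persistent | 47 | 0.084 | 0.863 |
| 18-month clock, onsets after day 270 | 50 | 0.053 | 0.832 |
| Day-270 clock, null 0.0117 | 50 | 0.059 | 0.843 |

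The constant-hazard row shows that the late window is not the cause of the shortfall. On the day-270 clock with its matching null, power reaches 0.90 at a true rate of about 25.5%. The printed 0.006/month fails on that clock because over 9 months it is only a rate of 1 − exp(−0.054) = 5.3%.

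**5. Size needed for the stated power.** On the 18-month clock, 70 patients with rejection at 12 or more give size 0.044 and power 0.908; 69 patients give power 0.898. That is above the cap of 50.

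**The case against.** The strongest reply is that nothing was miscalculated. Section 13.3.2 says that it relies on an asymptotic property, and the cited formula does return slightly more than 90% at the expected event count. That is true, and the point is best described as a small-sample shortfall. But the section presents 90% as the probability of rejecting, and the test it leads to does not have that probability.

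The alternative is also printed as a hazard. At 0.015/month for 18 months the rate is 23.66%, and power with 47 patients is then about 0.81 (18-month clock) to 0.84 (day-270 clock), or 0.86-0.87 with 50 evaluable. So the size of the shortfall depends on which input is used: across these inputs the chance of missing excess toxicity is about 13-22%. It still exceeds 10% throughout, and the criterion as stated is the 23% rate.

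The printed 12 is one case too many, enters no analysis, and does not cause the power loss. The clock mismatch is likewise a separate inconsistency, since 13.5.2 is explicit about its own clock and null. Both are minor, but they sit in the same derivation and can be corrected with it.

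Finally, 13.3.1 names estimation of the rate as the primary goal, and that goal is unaffected.

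**Conclusion.** The concern holds. With 47 evaluable patients and a true rate of 23%, the planned test rejects with probability 0.785 on the 18-month clock (size 0.041), or 0.815 on a day-270 clock with its matching null (size 0.056). The chance of not rejecting is about 18-22%, roughly double the 10% stated. No reading tested gives both a size of at most 0.05 and 90% power. Power of 90% is reached only at true rates of about 26.2% and 25.5% respectively.

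These figures assume complete follow-up to day 540 and a null hazard that matches the exposure window. The cut-off of 9 also assumes that onsets fall after day 270. Early-onset persistent toxicity changes little if it makes up half of the cases, and raises both power and size if it makes up all of them. With all 50 patients evaluable, power is about 0.83-0.84 with size 0.053-0.059. The 12-case figure is a separate wording slip. This should be fixed, but it does not affect the estimate of the toxicity rate.

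**What to change.** Keep 47 evaluable patients and the cap of 50, and revise the text as follows.

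1. State one clock in both 13.3.2 and 13.5.2, with the null hazard that belongs to it: 0.006/month over 18 months from treatment start, or about 0.0117/month over 9 months from day 270. The 18-month option leaves the test in 13.5.2 unchanged and keeps size below 0.05 when onsets fall after day 270.
2. Replace the 90% with exact or simulated operating characteristics for that clock. 18-month: size about 0.04, power about 0.78 at 23% and 0.90 at about 26%. Day-270: size about 0.056, power about 0.82 at 23% and 0.90 at about 25.5%.
3. If a case cut-off is printed (9 of 47 on the 18-month clock), say that it applies when onsets fall after day 270, because early-onset persistent cases can lower it. Distinguish it from the rule of 10 or more of 47 in section 14.2, which uses a broader toxicity definition.
4. Change the 12 required cases to about 11 expected cases.

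The cost is protocol wording and a less favourable stated power; the day-270 option would also show a size slightly above 0.05. No patients are added.

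### The phase II null hazard of 0.006/month fits 18 months at risk, but section 13.3.2 models 9 months from day 270 and section 13.5.2 mixes the two clocks

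*Combined protocol and SAP*

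**What the plan says.** **Derivation (13.3.2).** The model is set up as "Assuming an exponential distribution for time from the end of the acute period", which the section places at day 270, with 270 days of follow-up after it. On that basis "the hazard rate for the expected 10% toxicity rate and the unacceptable 23% toxicity rate is 0.006/month and 0.015/month", and "we require 12 cases with severe late GU/GI toxicity". This leads to 47 evaluable patients and 50 after a 5% allowance, for 90% power at one-sided 0.05.

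**Analysis (13.5.2).** Time to late toxicity is "defined as the time interval from start of protocol treatment to the date of onset of grade 3-5 GU/GI toxicity". Then: "The hazard rate will be estimated by the life table approach with a time span of 18 months". The log of the observed hazard is compared with the log of 0.006/month, with variance equal to one over the number of late cases. The section ends: "Because of the lead time of 9 months for the acute period, the 18-month late toxicity will be estimated by the 9-month toxicity rate", by cumulative incidence on the time just defined.

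**Follow-up limit (13.5.2).** One sentence says "The time analysis for recording severe late GU/GI toxicity for this protocol will be limited to 540 days from start of protocol therapy". The next says that, without an event, "the patient will be censored at the time of the analysis".

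**Endpoint (13.2.1).** Late toxicity is grade 3-5 GU or GI toxicity in days 270-540. Earlier toxicity counts only if it is still grade 3-5 after day 270.

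**The concern.** A hazard means a given percentage only over a stated time at risk. Section 13.3.2 states 9 months but prints hazards about half the size that 9 months requires. One of them, 0.006, is carried into 13.5.2 as the null value of the phase II primary test.

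Section 13.5.2 does not settle which clock applies. Its origin and 18-month span fit 0.006. Its lead-time sentence fits a clock started at day 270: a 9-month read-out from treatment start would capture only early toxicity that persisted, because new late events cannot begin before day 270. No single origin fits both the null hazard and the read-out. The verdict on whether late toxicity is excessive can therefore depend on which sentence the analyst follows.

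**Working it through.** **Inputs.** From 13.3.2: rates 10% and 23%, hazards 0.006 and 0.015/month, 12 cases, 47 patients, 5% loss, one-sided 0.05, 90% power. From 13.5.2: null 0.006/month, variance 1/D for D late cases.

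**Reproducing the plan's figures, hazard = -ln(1-p)/T**
- T = 18: -ln(0.90)/18 = 0.00585 and -ln(0.77)/18 = 0.01452, which round to the printed values.
- T = 9: -ln(0.90)/9 = 0.0117 and -ln(0.77)/9 = 0.0290.
- Cases: (1.645 + 1.282)²/(ln 2.5)² = 10.2, so 11; the plan prints 12.
- Patients: event probability at 0.015 over 18 months is 1 - exp(-0.27) = 0.2366; 11/0.2366 = 46.5, so 47; 47/0.95 = 49.5, so 50.

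The printed N is thus recovered with an 18-month span.

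**The printed hazards on the clock that 13.3.2 describes**
- 1 - exp(-0.006 × 9) = 5.3%; 1 - exp(-0.015 × 9) = 12.6%.
- Expected cases in 47 at 0.015/month: 47 × 0.1263 = 5.9 over 9 months, against 47 × 0.2366 = 11.1 over 18 months. The plan requires 12.

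**Effect on the test.** Assume 47 patients, all followed to day 540, no deaths, and onset at a constant hazard from day 270. With one life-table interval of t months, hazard = D/(t(47 - D/2)) and z = √D × ln(hazard/null); reject if z > 1.645.
- t = 18, null 0.006: D = 8 gives z = 1.54; D = 9 gives 2.02.
- t = 9, null 0.006: D = 5 gives z = 1.638; D = 6 gives 2.27.
- t = 9, null 0.0117: D = 8 gives z = 1.61; D = 9 gives 2.10.

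Rejection probabilities are binomial for the single interval. In brackets are simulated values with exact person-time.

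| Clock and null | Single interval rejects from | True rate 10% | True rate 23% |
|---|---|---|---|
| Treatment start, 0.006 | 9 cases | 0.041 (0.040) | 0.785 (0.784) |
| Day 270, 0.006 | 6 cases | 0.329 (0.414) | 0.974 (0.982) |
| Day 270, 0.0117 | 9 cases | 0.041 (0.056) | 0.785 (0.81) |

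With exact person-time on the day-270 clock and null 0.006, 5 cases reject in about 46% of such trials.

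**Opposite verdicts.** For the same data, the day-270 clock with 0.006 rejects whenever the treatment-start clock does, so the chance of disagreement is the difference between the first two rows.
- At 10%: 0.329 - 0.041 = 0.29, or 0.414 - 0.040 = 0.37.
- At 23%: 0.974 - 0.785 = 0.19, or 0.982 - 0.784 = 0.20.

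**Sample size after correction.** The hazard ratio is 0.0290/0.0117 = 2.48 instead of 2.5. Cases: (1.645 + 1.282)²/(ln 2.48)² = 10.4, so 11; 11/0.23 = 47.8, so about 48.

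**The case against.** The analysis section governs the test, and its origin, span, 540-day limit and null agree with one another. Read literally, it rejects from 9 cases with probability 0.041 at 10%. In the single-interval calculation, the corrected constants on either clock give the same rule. The inflated error arises only if someone takes the planning clock from 13.3.2 and keeps 0.006. The upper figures (0.41, and rejection at 5 cases) also use exact person-time, whereas 13.5.2 names a life table; with one interval the disputed results are 6 to 8 cases. A corrected derivation gives 48 patients, and 48/0.95 = 50.5 exceeds the cap of 50.

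Much of this stands: the literal test is calibrated and the harm is conditional. It does not remove the point. Day 270 is the only origin named in the derivation that produced 0.006, and the lead-time sentence in 13.5.2 points to it. Section 13.5.2 gives no interval width, and finer intervals move the result towards exact person-time, so a range is fair. On the cap, 48 comes from rounding cases up before dividing. Unrounded, 10.4/0.23 = 45.2, and 47 patients at 23% give 10.8 expected cases and approximate power 0.91 by the plan's own formula. The rejection probability of 0.785 at 23% falls short of 90%, but that is a separate issue, present under the literal test too.

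**Conclusion.** The point holds and should be fixed. The hazards in 13.3.2 are wrong for the clock it describes by a factor of about two, and 13.5.2 uses another origin without reconciling its null hazard with its read-out. Followed literally, the 13.5.2 test is sound. If exposure is counted from day 270 with null 0.006, the chance of rejecting a treatment with the acceptable 10% rate rises from 0.04 to 0.33-0.41. At 10%, 4.7 cases are expected in 47, so results of 5 to 8 cases are realistic. The hazard ratio and patient number hardly move. The figures rest on 47 patients followed to day 540, a constant hazard after day 270, and no dropout or competing deaths.

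Two smaller gaps follow. Persisting toxicity is dated by an onset that precedes time zero in 13.3.2. Censoring at the analysis date conflicts with the 540-day limit: with accrual over three to four years, early patients will have been followed well beyond it.

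**What to change.** Name one origin and use it in both sections.
- **Day 270:** null 0.0117 and alternative 0.0290/month; cumulative incidence read at 9 months; grade 3-5 toxicity persisting at day 270 counted as an event on that day.
- **Treatment start:** null 0.00585 and alternative 0.0145/month; cumulative incidence of late events read at 18 months. These are then average rates over 18 months, since new late events cannot occur in the first nine. Day 270 therefore suits the exponential model better.

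State the origin in the read-out sentence. Censor at the earlier of day 540 and the last assessment. For the hazard test, end exposure at death; in the cumulative incidence, treat death as a competing event.

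The cost is wording and constants in 13.3.2 and 13.5.2. No new data are needed, and the 50-patient size can stay.
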